i) Psychophysiological Measures: These will include heart rate and blood pressure monitored using a Critikon Dinamap while skin temperature will be measured using Yellow Springs Instruments 4600 precision thermometer. The cuff of the Dinamap will be on the subject's dominant arm while the probe of will be attached to the middle finger of the subject's non-dominant arm. These data will be further used to examine the safety of using the medication combination during alcohol self-administration.

4. **Statistical Considerations:** Describe the statistical analyses that support the study design.

All outcomes will be summarized descriptively and assessed for normality prior to analysis using normal probability plots and Kolmogorov test statistics. Transformations or nonparametric analyses will be performed as necessary. In the mixed models described below, the correlation between repeated measures on an individual will be modeled using random effects and/or structured variance-covariance matrices. The best-fitting variance-covariance structure will be determined by information criterion. The mixed-effects approach is advantageous in that it is unaffected by randomly missing data and allows greater flexibility in modeling the correlation structure of repeated-measures data (Gueorguieva and Krystal, 2004). In the models below, we will test for order effects, although any such effects should be greatly minimized with the inclusion of the baseline session. All tests will be two-sided and considered statistically significant at alpha=.05. Significance levels for secondary comparisons will be adjusted for multiple tests using the Bonferroni correction, basing the adjustment on the number of conceptually related statistical tests within each hypothesis.

**Aim 1:** Total number of drinks consumed during the self-administration period will be compared among treatment conditions using linear mixed models with treatment (NTX vs. NTX+MEM/NAC) included as a within-subjects factor. In these models, we will also consider baseline drinking, as assessed by using the 90 day TLFB obtained at intake, as a potential covariate. Non-significant covariates will be dropped for parsimony. A significant treatment effect, where total number of drinks is reduced during combination NTX+MEM/NAC treatment compared to NTX alone, will be supportive of our hypothesis. Secondary measures of alcohol-drinking typology such as average time to consume each drink and inter-sip interval will be analyzed using similar models as described above, whereas time to first drink during the ad-lib drinking period will be analyzed using survival models with subject-specific frailties to account for correlation of the repeated survival outcomes within individuals.

**Aim 2:** Scores on the Yale Craving Scale will be the primary outcome in this aim and will represent the dependent variable in a linear mixed model evaluating combination treatment effects of NTX and MEM/NAC on alcohol craving. The model will include treatment (NTX vs. NTX+MEM/NAC) and time (see study time points, Table 1) as within-subjects explanatory factors, and random subjects effects. The interaction between treatment and time will be modeled and interpreted using graphical displays and appropriate post-hoc tests. We anticipate a significant treatment by time interaction explained by greater reductions in craving over time among combination NTX+MEM/NAC compared to NTX alone. A secondary measure of craving, the Alcohol Urge Questionnaire, will be analyzed using the same model described above. We will also explore the influence NTX vs. NTX+MEM/NAC on YCS alcohol craving in response to the alcohol cue exposure just prior to the start of the priming drink period using a similar model.

**Aim 3:** Alcohol-induced stimulation, measured by the Biphasic Alcohol Effects Scale (BAES), will be analyzed using the same model described for alcohol craving in Aim 2. A significant treatment by time interaction, explained by reduced alcohol stimulation to due to combination

NTX+MEM/NAC treatment, compared to NTX alone, will be supportive of our hypothesis. A secondary analysis will conduct similar comparisons on the sedation scores obtained using the BAES.

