*Yale Craving Scale (YCS)*: We have been collaborating with [name] to develop this craving measure based on psychophysiological scaling methods. In her work on individual differences in the ability to taste bitterness, [name] and colleagues (Marks et al., 1988) used magnitude-matching procedures (Stevens and Marks, 1980) in which participants matched the intensity of perceived bitterness to sounds. By doing so, the problem of differences in how labels (e.g., very strong) are applied was circumvented by making the comparison to a standard that is unrelated to taste. The resulting scale, Labeled Magnitude Scale (gLMS) (Bartoshuk, 2002), has been extended to measure hedonic ratings for foods, and we have adapted it for rating craving for tobacco and alcohol. It is not subject to the ceiling effects that often occur in craving research (Sayette et al., 2000). We have been collecting craving data using this scale in our ongoing projects and the findings from this scale have been found to parallel those obtained using the Alcohol Urge questionnaire. *A significant advantage of this scale is that following completion of baseline training to match perceived intensity of craving to the perceived brightness from the sun, each assessment timepoint only consists of a single visual analog scale of craving, making it very easy to administer.*

f) Clinical Institute Withdrawal Assessment for Alcohol-Revised (CIWA-Ar): This is a modified, shorter version of the Clinical Institute Withdrawal Scale for Alcohol which is equally efficient and reliable as the original scale without a significant loss in accuracy. The CIWA-Ar is a 10 item scale that contains alcohol withdrawal signs and symptoms that include nausea/vomiting, tremor, headache, anxiety, agitation, orientation, sweating, and auditory, visual, and tactile disturbances. This tool often guides the clinical management of alcohol (Sullivan et al., 1991) withdrawal (for a review, see Saitz and O'Malley, 1997) and is used extensively in research on alcohol withdrawal (Sellers et al., 1991; Saitz et al., 1994).

g) Psychiatric and mood symptoms: We will assess changes in these symptoms during Days 1-13 using:

*Positive and Negative Syndrome Scale (PANSS)* (Chapman et al., 1980): A clinician-rated general assessment measure used to measure psychosis (positive symptoms), emotional or motivational deficits (negative symptoms), and thought disorder.

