### ***Power Analysis***

This is a pilot trial and we will use the data to determine initial tolerability and effect size estimates for future trials. We will recruit a total of 30 completers in this trial, 10 in each group.

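### Secondary comparisons are adjusted by single-step Bonferroni; Holm's step-down procedure holds the same 5% family-wise error, never rejects less, and gains power when more than one effect in a family is real

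*Combined protocol and SAP*

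**What the plan says.** Section V, item 4 (Statistical Considerations) sets the general level: "All tests will be two-sided and considered statistically significant at alpha=.05". For multiplicity it then says: "Significance levels for secondary comparisons will be adjusted for multiple tests using the Bonferroni correction". The size of each family is not given as a number; it is to follow from how many related tests fall under a given hypothesis. No other multiplicity rule appears in the document.

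The analyses that the rule reaches are described aim by aim in the same section:

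- **Aim 1:** "Secondary measures of alcohol-drinking typology such as average time to consume each drink and inter-sip interval" are analysed with mixed models like the primary one. Time to first drink is analysed with a frailty survival model. That makes three named secondary measures.
- **Aim 2:** one secondary craving measure, the Alcohol Urge Questionnaire.
- **Aim 3:** one secondary analysis, the sedation scores of the Biphasic Alcohol Effects Scale.

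The Power Analysis calls the study a pilot for tolerability and effect-size estimates, gives no power target, and says: "We will recruit a total of 30 completers in this trial, 10 in each group".

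**The concern.** Bonferroni holds every test in a family of m to 0.05/m, even after some hypotheses in that family have been rejected. Holm relaxes the threshold as rejections accumulate and keeps the same family-wise guarantee. It needs only the p-values, so it can be used across the mixed models and the survival model of Aim 1.

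The Aim 1 secondary measures describe the manner of drinking within one session, so a treatment that changes one may well change the others. Holm helps in that situation. In a trial with about 30 completers, a real difference on the second or third measure is more likely to be reported as non-significant under Bonferroni than it needs to be. The primary tests are not affected.

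**Working it through.** **The plan's own figures.** Three groups of 10 give 3 × 10 = 30 completers, which agrees with the Power Analysis. No power, effect size, SD or correlation is stated, so there is no planned power to reproduce.

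**Why Holm is never worse.** Order the p-values within a family from smallest to largest. Holm compares the k-th smallest with 0.05/(m − k + 1) and stops at the first failure. For m = 3:

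| Step | Bonferroni | Holm |
|---|---|---|
| smallest p | 0.05/3 = 0.0167 | 0.05/3 = 0.0167 |
| second | 0.0167 | 0.05/2 = 0.025 |
| largest | 0.0167 | 0.05/1 = 0.05 |

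Any p-value at or below 0.0167 also passes under Holm, so Holm rejects at least as much.

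**Why the error rate stays at 5%.** Suppose m0 of the m null hypotheses are true. The first true null that Holm rejects can come no later than step m − m0 + 1, so its threshold is at most 0.05/m0. The chance that any of the m0 true nulls falls below that is at most m0 × 0.05/m0 = 0.05, whatever the dependence between tests.

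**Size of the gain: assumptions.**

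- There are 30 completers. Each takes two of the three conditions, because Section V, item 3 has two medication phases. The 10 per group are read as 10 on each pair of conditions.
- With SD σ of the within-person difference, a contrast has direct information 10/σ². The indirect route through the third condition has variance 2σ²/10, so it adds 5/σ². The total is 15/σ², or 15 pair-equivalents.
- Thirty differences less two treatment parameters and one period parameter leave 27 degrees of freedom.
- m = 3, correlation 0.5 between tests, and d = 0.8 in units of σ. The noncentrality is 0.8 × √15 = 3.10.

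The two-sided critical values of t on 27 df at levels 0.0167, 0.025 and 0.05 are 2.55, 2.37 and 2.05. Bonferroni uses 2.55 throughout, and its power per real effect is 70.5%. Simulation of the joint t statistics gives the average power per real effect:

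| Real effects (of 3) | Bonferroni | Holm |
|---|---|---|
| three | 70.5% | 78% |
| two | 70.5% | 74% |
| one | 70.5% | 70.6% |

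With all three real, power to show all three goes from 49% to 67%. The chance of at least one rejection is then identical, because Holm's first step is Bonferroni. At d = 0.6 with all three real, average power goes from 42% to 49%.

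**Sensitivity to the design assumptions.** A separate simulation used simple paired t tests with 10, 20 or 30 pairs, m of 2 to 4, correlation of 0 to 0.8, and d of 0.5 or 0.8:

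- Across the grid, Holm's gain in average power is about 1 to 11 percentage points when all effects are real, and 0 to 0.4 points when one is.
- With 30 pairs, m = 3, correlation 0.5 and d = 0.5, average power goes from 58.3% to 66.9% with all effects real, and stays at 58.4% with one.
- With 10 pairs, m = 2, correlation 0.5 and d = 0.8, all effects real, it goes from 47.2% to 53.7%.

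**The case against.** **Bonferroni is valid and prespecified.** This stands. No error rate is breached, no primary conclusion changes, and with no power target for secondary tests no stated goal is missed.

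**The gain can be small or nil.** This also stands. If only one effect in a family is real, Holm adds almost nothing. If the single secondary measures of Aims 2 and 3 each form a family of one, the two methods coincide. In Aim 1, Section V, item 1 lists time to first drink and average time per drink under an exploratory hypothesis. Time to first drink has a survival analysis, which the t-test simulation does not represent exactly. The figures are therefore illustrative, while the ordering of the two methods holds regardless.

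**Holm lacks simple matching simultaneous intervals.** This is true, and it counts for something in a pilot meant to estimate effects. Intervals of another kind can be reported beside Holm p-values, so the loss is minor. It is still a reason not to say that Bonferroni gives up power for no return.

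**Time-point contrasts.** A reader might infer that Bonferroni also governs the contrasts at individual times in Aims 2 and 3, and that a correlation-based (max-t) adjustment over all 17 Yale Craving Scale times in Table 1 would recover much more power. The documents do not support this. The Bonferroni sentence names secondary comparisons only. For the interaction the plan says no more than "The interaction between treatment and time will be modeled and interpreted using graphical displays and appropriate post-hoc tests", with no method named. Nor does the text say that all 17 times would form one family. The Aim 2 hypothesis concerns the self-administration period, for which Table 1 has four such ratings (4:30, 5:30, 6:30 and 7 pm). Power figures for a 17-time Bonferroni correction would describe a procedure that the plan does not contain.

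**Conclusion.** The point holds as a matter of efficiency for the secondary comparisons. That Holm is at least as powerful at the same 5% family-wise error depends on no assumption about effects, correlation or sample size. It would hold equally with the 86 participants given under Targeted Enrollment, a number that itself needs reconciling with the 30 completers.

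The size of the gain does depend on assumptions. With 15 pair-equivalents, 27 df, three measures, correlation 0.5 and d = 0.8, average power rises by about 8 points if all three effects are real and by 3 to 4 points if two are, and hardly at all if one is. The practical benefit is largely confined to Aim 1's secondary drinking measures. The point does not extend to the post-hoc time-point contrasts, and it does not imply that any result under the present rule would be invalid.

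**What to change.** In the multiplicity sentence of Section V, item 4, name the Holm step-down procedure instead of the Bonferroni correction. Leave the definition of the families and the 5% level as they are. Add that unadjusted or Bonferroni confidence intervals will be reported beside the Holm-adjusted p-values, and say which.

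The cost is a short change of wording, made before the data are analysed. It needs no new data and no software beyond the p-values already planned. The small downside is that a Holm rejection and the reported interval may not always agree, so the text should say that the adjusted p-value decides significance.

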In the current proposal we would like to conduct an important extension of this work. We will test the hypothesis that by targeting both opioidergic and glutamatergic mechanisms, one may synergistically target multiple neurochemical and behavioral processes, leading to optimal reduction of alcohol drinking. This pilot trial will be conducted in FHP drinkers in whom we have observed reduction in alcohol reward with MEM and in alcohol drinking with NTX. We will test the efficacy and tolerability of the combined use of MEM and NTX. We will also test the efficacy and tolerability of the combined use of N-acetyl cysteine and NTX. N-acetylcysteine (NAC), an acetyl pro-drug of cysteine is another agent which can be used to target the glutamatergic system. NAC is believed to produce its effects by stimulating the cysteine-glutamate exchanger and thus altering synaptic glutamate levels. A significant potential advantage of NAC is better tolerability, which may make it a better glutamate-altering agent to use in combination with NTX. Finally, we will also evaluate the predictive utility of impulsive responding, implicit alcohol motivational tendencies, and variations in genes for opiate receptors and for signal transduction proteins linking dopamine and glutamate receptors upon alcohol drinking behaviors.

The following specific aims will be tested:

**Primary Aim 1:** Evaluate the effects of pretreatment with a combination of naltrexone (NTX; 50 mg) and memantine (MEM; 20 mg) or N-acetylcysteine (NAC; 2400 mg) on drinking in FHP drinkers.

*Primary Hypothesis:* Combination treatment with NTX and MEM or NAC, when compared with NTX alone, will reduce number of drinks consumed during the self-administration period.  
*Exploratory hypothesis:* Combination treatment with NTX and MEM will reduce time to first drink and increase the average time to consume each drink, during the self-administration phase.

**Primary Aim 2:** Evaluate the effects of pretreatment with a combination of naltrexone (NTX; 50 mg) and memantine (MEM; 20 mg) or NAC (2400 mg) on alcohol craving in FHP drinkers  
*Hypothesis:* Combination treatment with NTX and MEM or NAC, when compared with NTX alone, will reduce alcohol craving (Yale Craving Scale) during the self-administration period  
*Exploratory hypothesis:* Combination treatment with NTX and MEM will reduce craving in response to the alcohol cue presented just prior to the priming drink period.

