**Primary Aim 3:** Evaluate the effects of pretreatment with a combination of naltrexone (NTX; 50 mg) and memantine (MEM; 20 mg) or NAC (2400 mg) on alcohol-induced stimulation in FHP drinkers.

*Hypothesis:* Combination treatment with NTX and MEM or NAC, when compared with NTX alone, will reduce alcohol-induced stimulation (Biphasic Alcohol Effects Scale) during the self-administration period.

**Secondary Aim:** Examine the tolerability of co-administration of NTX and MEM and NTX and NAC

**Exploratory Aims:** Examine the influence of innovative predictors of treatment response, including:

- ❖ Impulsive propensity and implicit alcohol associations
- ❖ Opioidergic (OPRM1) and signal transduction proteins that moderate the function of NR2B-containing NMDA receptors (Fyn kinase, STEP) genotypes
- ❖ Pavlovian to Instrumental transfer propensity

2. **Background:** Describe the background information that led to the plan for this project. Provide references to support the expectation of obtaining useful scientific data.

Alcohol use, abuse, and dependence are a huge public health problem in the United States and worldwide. Epidemiological evidence suggests that almost 17.6 million adults in the U.S. are abusing alcohol or are alcohol dependent (Grant et al., 2004), emphasizing the importance of developing optimal interventions for the treatment of this disorder. At present, three medications have been approved by the FDA in the U.S. for the treatment of alcohol dependence: disulfiram, naltrexone, and acamprosate. However, the treatments effects for these agents range from minimal to modest, and they are minimally utilized in clinical community settings (Garbutt et al., 1999; Krishnan-Sarin et al., 2009b). Therefore, there is a significant need for other medications, or combinations of medications, that are more efficacious in reducing alcohol use.

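### Aims 2 and 3 hypothesise lower craving and stimulation during self-administration, but the result named for each is a treatment-by-time interaction over Table 1 times that are not limited to that period

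*Combined protocol and SAP*

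**What the plan says.** **Hypotheses (Section V, item 1).** Under Primary Aim 2, combination treatment compared with naltrexone (NTX) alone "will reduce alcohol craving (Yale Craving Scale) during the self-administration period". Under Primary Aim 3 it "will reduce alcohol-induced stimulation (Biphasic Alcohol Effects Scale) during the self-administration period". Craving after the alcohol cue is a separate, exploratory hypothesis: the combination "will reduce craving in response to the alcohol cue presented just prior to the priming drink period". The Alcohol-Drinking Paradigm section places self-administration in three one-hour blocks from 4 to 7 pm.

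**Analysis (Section V, item 4).** The Aim 2 mixed model has treatment and "time (see study time points, Table 1) as within-subjects explanatory factors, and random subjects effects". Its named result is: "We anticipate a significant treatment by time interaction explained by greater reductions in craving over time among combination NTX+MEM/NAC compared to NTX alone". The interaction is to be interpreted with graphs and post-hoc tests that are not defined. Aim 3 uses the same model, and the result that would support its hypothesis is "A significant treatment by time interaction, explained by reduced alcohol stimulation to due to combination" treatment compared with NTX alone. The cue question gets its own similar model for "YCS alcohol craving in response to the alcohol cue exposure just prior to the start of the priming drink period".

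Aim 1 is different. "Total number of drinks consumed during the self-administration period will be compared among treatment conditions", and the supporting result is a treatment effect on that outcome.

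**Power Analysis.** The trial is a pilot meant to give tolerability and effect-size estimates, with 30 completers, 10 per group. No effect size, standard deviation or power is stated.

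**The concern.** A hypothesis about the level of craving or stimulation in one window is answered by a treatment difference in that window. A treatment-by-time interaction asks whether the treatment difference varies across the ratings, wherever that variation lies. The two can disagree in both directions:

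- Craving may be lower at every rating, SA hours included, with no interaction. This is not a contrived case. Subjects reach the session after about a week of dosing, so a shift could already be present in the morning.
- The interaction may be significant because of the pre-alcohol, priming or late-evening ratings, with no difference between 4 and 7 pm.

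A primary aim could therefore be reported as supported, or not, on a result that does not address its hypothesis. An omnibus interaction also gives no single effect size to carry into a later trial, which is the pilot's stated purpose.

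**Working it through.** The plan states no figure for these aims, so there is none to reproduce.

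**1. Count of Table 1 ratings**

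| Window | YCS | n | BAES | n |
|---|---|---|---|---|
| Before alcohol | 10:00 am; 2:00, 2:30, 2:45, 2:59 pm | 5 | 2:00, 2:30 pm | 2 |
| Priming hour | 3:10, 3:20, 3:30, 3:50 | 4 | 3:10, 3:30, 3:50 | 3 |
| SA, 4 to 7 pm | 4:30, 5:30, 6:30, 7:00 | 4 | 4:30, 4:55, 5:30, 5:55, 6:30, 7:00 | 6 |
| After | 8, 9, 10 pm; 7 am | 4 | 8, 9, 10 pm | 3 |
| Total | | 17 | | 14 |

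Outside SA: YCS 13/17 = 76%, BAES 8/14 = 57%. If the 7 pm rating is not counted as SA: 14/17 = 82% and 9/14 = 64%. Among post-alcohol BAES ratings, 6 of 12 are inside.

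The paradigm section says craving is assessed every thirty minutes in the choice hours, while Table 1 shows no YCS at about 5 and 6 pm (the Alcohol Urge Questionnaire is listed there). If YCS were added at both times, 13/19 = 68% would still lie outside.

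**2. What the interaction responds to**

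Take a drop of fixed size at m of T ratings, with exchangeable within-session residuals. The interaction noncentrality is proportional to m(T − m)/T, whatever the sample size.

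- YCS, all 17 ratings: 17 × 0/17 = 0
- YCS, SA only, priming only or late only: 4 × 13/17 = 3.06 each
- YCS, pre-alcohol only: 5 × 12/17 = 3.53
- BAES, SA only: 6 × 8/14 = 3.43
- BAES, the six post-alcohol ratings outside SA: 6 × 8/14 = 3.43
- BAES, all 12 post-alcohol ratings: 12 × 2/14 = 1.71

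The zero for a constant shift holds under any residual correlation. The ranking of windows does not. With AR(1) residuals by rating order (rho 0.3 to 0.7), the YCS values are SA 2.33–3.32, priming the same, pre-alcohol 2.04–2.36 and late 1.89–2.16. Pre-alcohol is level with SA at rho 0.3 (2.36 against 2.33), but both it and late fall below SA at 0.5 and 0.7. They stay well above zero.

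**3. Illustrative power (assumed values, not from the documents)**

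Assume 10 subjects on each of the three pairs of conditions. For one combination against NTX, the direct pair carries information 10 and the indirect route 5, so the variance factor is 1/15, with 30 − 2 = 28 df. Assume a drop of 0.5, total SD 1, subject variance 0.4, and session/residual variances 0.1/0.5, 0.2/0.4 or 0.3/0.3. Tests are two-sided at 0.05.

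Example: YCS, SA-only drop, variances 0.2/0.4.
- Interaction: noncentrality 0.25 × 3.06/(0.8/15) = 14.3 on 16 df; power 62%.
- SA contrast: variance (0.4 + 0.8/4)/15 = 0.04, SE 0.2, ratio 0.5/0.2 = 2.5; power 67%.

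| Where the drop lies | Interaction | SA contrast* |
|---|---|---|
| YCS, all 17 ratings | 5% | 58–80% |
| YCS, SA only | 50–78% | 58–80% |
| YCS, priming only or late only | 50–78% | 5% |
| YCS, pre-alcohol only | 58–85% | 5% |
| BAES, all 12 post-alcohol | 30–51% | 63–84% |
| BAES, SA only | 60–87% | 63–84% |
| BAES, six post-alcohol outside SA | 60–87% | 5% |

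*For BAES, change from the 2:00/2:30 pm ratings.

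With 28 per pair (about 86/3, from the enrolment target), the first row is still 5% for the interaction, against 96–100% for the contrast.

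**The case against.** **The model can already answer the question.** It contains a treatment term, SA-period means can be estimated from it, and post-hoc tests are foreseen. This stands: the SA difference is estimable, and a reader who infers that the plan cannot recover it goes too far. But that difference is not the named result. The post-hoc tests have no stated window and serve to interpret an interaction, which a uniform reduction would not produce.

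**Table 1 is only a pointer.** A reader might infer that all 17 YCS ratings, including the 2:59 pm post-cue rating, are certain to enter the primary model. The text cites the Table 1 time points without saying every row is used, and the cue response has its own model. What can be said is that nothing is excluded.

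**Aim 3 is not the same case.** This largely stands. The outcome is alcohol-induced stimulation, so including pre-alcohol ratings is reasonable, and the criterion requires reduced stimulation, which fixes the direction. A purely pre-alcohol difference would not fit it. For an SA-only BAES effect the illustration shows no material loss of power. What remains is that the criterion does not separate SA-period from priming or late differences.

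**SA ratings are not a clean drug effect.** They depend partly on how much each subject chose to drink, which is the Aim 1 outcome. The priming dose exists to give a standard exposure. This is a real cost of the SA contrast. Rewording the hypotheses would be another consistent repair, but as written they name the SA period.

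**Conclusion.** The concern holds, clearly for Aim 2 and more weakly for Aim 3. The hypotheses are tied to 4 to 7 pm, the named result is not, and no SA-period contrast is specified.

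Two results need no assumed effect size or sample size: the rating counts (13 of 17 YCS and 8 of 14 BAES outside SA), and the roughly 5% rejection rate of a valid interaction test when craving falls equally at every rating. That a difference confined to another window can make the interaction significant follows from the form of the test; how easily it does so depends on the residual correlation. The documents do not support a stronger reading that the interaction is always as sensitive outside SA as inside it.

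The power figures rest on an assumed effect, variances and split of the 30 completers. They illustrate the mismatch and do not estimate this trial's power. In a pilot with no power claim this is a wording correction worth making, not a flaw in the data collected.

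**What to change.** **Aim 2.** Name as the primary test the 1-df treatment difference in mean YCS over all SA-period ratings, taken from the planned mixed model, with its confidence interval.

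**Aim 3.** Name the SA-period contrast on BAES stimulation, as change from the 2:00/2:30 pm pre-alcohol ratings, with its confidence interval. Give the raw SA-period mean as a sensitivity analysis.

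**Both.** Keep the full-session interaction as secondary, and report the priming-period contrast alongside it as secondary. Reconcile the thirty-minute craving schedule in the paradigm section with the YCS entries in Table 1, and state whether the 7 pm rating counts as SA.

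**Cost.** Plan wording only; no new data. Three downsides should be stated:
- The interaction can be more powerful for some SA-only effects (at variances 0.3/0.3: YCS 78% against 58%, BAES 87% against 84%).
- The Aim 3 change contrast misses a shift already present before alcohol, hence the raw-mean sensitivity analysis.
- SA-period ratings partly reflect how much was drunk, hence the priming-period contrast.
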